9.4 Subject Disposition and Characteristics

Subject disposition and demographic characteristics will be presented by treatment group and overall. Frequencies and percentages will be used to present the number of subjects that

participated in each phase of the study (Tolerance Phase and Treatment Phase), the number that completed the study, number of subjects withdrawn as well as the reason of withdrawal if that is provided. Demographic characteristics of the subjects such as gender, race and menopausal status will be presented using frequencies and percentages. The age of the subjects, height, weight and BMI will be presented using summary statistics (mean, standard deviation (SD) median, minimum and maximum). Any other baseline characteristics will be presented using either frequencies and percentages or summary statistics, as appropriate.

9.5 Statistical Analyses

9.5.1 Primary Endpoint(s)

9.5.1.1 Primary Analysis

The primary endpoint for the clinical investigation is the change from baseline in Total FSFI score assessed at the end of the 4-week IP use period. An increase of at least 4 points in the FSFI score from baseline to 4-weeks post-lubricant use is considered a clinically important change. The change score will be calculated by subtracting the score at the end of the 4-week run-in period (baseline) from the score at the end of the 4-week IP use period. A positive change value indicates an improvement in sexual function.

The FSFI questionnaire (Appendix A) consists of 19 items across six domains. The answer choices in the FSFI carry a number of points and are summed to obtain six domain (subscale) scores and an overall score. The domain scores are obtained as the sum of points attributed to questions in that domain multiplied by the domain factor.

The following table describes the six domains, their corresponding items and possible range, as well as the domain factor.

Table 9-1 Female Sexual Function Index Domain Scores and Full-Scale Score

Domain	Items	Score range	Factor	Min score	Max score
Desire	1, 2	1 - 5	0.6	1.2	6
Arousal	3, 4, 5, 6	0 - 5	0.3	0	6
Lubrication	7, 8, 9, 10	0 - 5	0.3	0	6
Orgasm	11, 12, 13	0 - 5	0.4	0	6
Satisfaction	14, 15, 16	0/1 - 5	0.4	0.8	6
Pain	17, 18, 19	0 - 5	0.4	0	6
Scale range				2	36

For the primary analysis, the Total FSFI Score at Visit 3 of the Treatment Phase is compared to its baseline value using a paired t-test. The statistical testing is carried out separately for each IP and consequently a single null and alternative hypothesis is defined for each IP. This results in two individual hypothesis pairs, which apply analogously to the following example for both IPs:

H_0 : The Total FSFI score at Visit 3 of the Treatment Phase shows no difference from the corresponding baseline score.

H_1 : The Total FSFI score at Visit 3 of the Treatment Phase shows a difference from the corresponding baseline score.

These hypotheses are expressed mathematically by

$$H_0: \mu_{\text{Baseline}} = \mu_{V3}$$

$$H_1: \mu_{\text{Baseline}} \neq \mu_{V3}$$

where μ_{Baseline} is the mean total FSFI Score at Baseline and μ_{V3} is the mean total FSFI Score at Visit 3 of the Treatment Phase.

Since the primary endpoint is being evaluated for each product separately, the resulting p-values will be compared to a critical alpha threshold that will be adjusted according to the Bonferroni-Holm method to ensure the Family Wise Error is controlled at 5%. For each treatment group, the Total FSFI will be summarised as actual scores at baseline and at 4 weeks, as well as change from baseline, using N, mean, standard deviation (SD), standard error (SE), median, minimum and maximum. The mean change from baseline in Total FSFI will also be presented with Bonferroni-corrected 97.5% confidence intervals (CI) to account for the 2 treatment comparisons. If the within-subject differences are not Normally distributed, a Wilcoxon signed rank test will be used to compare the change from baseline. In this case, Hodges-Lehmann 97.5% confidence intervals will be calculated.

Additionally, the number and percentage of subjects (including a 95% confidence interval calculated using the Wilson score method) achieving a 4-point improvement in Total FSFI at 4 weeks will be presented by treatment group. This will indicate the percentage of subjects who achieve the pre-defined MCID.

The handling of missing response on the FSFI is described in [Section 9.8](#).

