9.3 Analysis Datasets

The Full Analysis Set (FAS) will include all randomised subjects who enter the Treatment Phase of the study. The FAS will be used to assess the primary endpoint and all other endpoints that are assessed during the Treatment Phase, with the exception of adverse events. Subjects will be assigned to treatment to which they were randomised.

For the FSFI (total score and percentage of subjects achieving at least a 4-point change in total score), an analysis will also be performed on the Per Protocol (PP) population. The PP population will exclude subjects who have not been compliant with the requirements of at least one coital act per week during both the run-in and 4-week IP use period of the Treatment Phase, as well as using IP at least once per week for penile/vaginal intercourse during the treatment period. In addition, subjects who use less than 80% of their assigned product (<9.6g) will be removed from the PP population. Subjects may be excluded from the PP population due to other reasons that may impact the evaluation of study products and these will be identified prior to database lock. Subjects will be assigned to treatment received.

The Safety Population will include all randomised subjects and will include subjects who take part in the Tolerance Phase and/or the Treatment Phase. The Safety Population will be used for producing demographic, adverse event and other safety tables. Subjects will be assigned to treatment received.

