9.5.1.2 Secondary Analysis

The analyses described in [Section 9.5.1.1](#) will be repeated for the PP population. In addition, for each treatment group, the Total FSFI will be summarised as actual scores at baseline and at 4 weeks, as well as change from baseline for the pre- and post-menopausal subgroups (using the FAS population). No hypothesis testing will be performed for the subgroup analyses.

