9.5.2 Secondary Endpoints

9.5.2.1 Secondary Endpoint Analyses

For each of the secondary endpoints, hypothesis testing will not be performed, unless stated otherwise. Since the secondary endpoints are for supportive evidence only, no adjustments to p-values will be made.

The secondary endpoints are:

Treatment Phase:

- Number and percentage of subjects who achieve at least 4-point increase in total FSFI between baseline and 4 weeks.

For each treatment group and overall, the number and percentage of subjects who achieve an improvement of at least 4 points in the FSFI total score will be determined. The percentage and the 95% CI based on the Wilson Score method will be presented.

- Number and percentage of subjects who transition from sexual dysfunction (≤ 26.55 total FSFI score) to sexual function (> 26.55 total FSFI score) between baseline and 4 weeks.

For each treatment group and overall, the number and percentage of subjects who transition from sexual dysfunction (≤ 26.55 total FSFI score) to sexual function (> 26.55 total FSFI score) between baseline and 4 weeks will be determined. Also, the number of subjects categorised as sexual function at 4 weeks will be compared to the number categorised as sexual function at baseline, using McNemar's test. This comparison will be performed by treatment group and overall.

- Change from baseline in the FSFI individual domain scores (desire, arousal, lubrication, orgasm, satisfaction, and pain) at 4 weeks.

For each treatment group, the FSFI individual domain scores will be summarised as actual scores at baseline and at 4 weeks, as well as change from baseline, using n, mean, standard deviation (SD), median, minimum and maximum. Also, for each treatment group, the scores at 4 weeks will be compared to baseline using a paired t-test or Wilcoxon signed rank test, as appropriate.

For this secondary endpoint, the following pairs of hypotheses apply, formulated analogously for all domain scores:

H_0 : The FSFI domain score at Visit 3 of the Treatment Phase shows no difference from the corresponding baseline score.

H_1 : The FSFI domain score at Visit 3 of the Treatment Phase shows a difference from the corresponding baseline score.

Since testing is done within the non-confirmatory secondary endpoints, there is no adjustment for multiple testing.

- SPQs after first use at home and after 4 weeks

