9.6 Description Statistics and Listings

Data related to the primary and secondary endpoints will be summarised using descriptive statistics where appropriate, and subject-level data will be provided in data listings.

Product usage will be summarised using descriptive statistics (total amount used and number of times product was used). Sexual activity will be summarised using descriptive statistics.

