13. Over the past 4 weeks, how satisfied have you been with your ability to reach an orgasm (climax) during sexual activity or intercourse?

0 = No sexual activity
5 = Very satisfied
4 = Satisfied
3 = Neither satisfied/dissatisfied
2 = Dissatisfied
1 = Very dissatisfied

Copyright ©2000 All Rights Reserved

FSFI - UK English - Final version - 17 Jan 07 - Mapi Research Institute.
03296

14. Over the past 4 weeks, how **satisfied** have you been with the amount of emotional closeness between you and your partner during sexual activity?

0 = No sexual activity
5 = Very satisfied
4 = Satisfied
3 = Neither satisfied/dissatisfied
2 = Dissatisfied
1 = Very dissatisfied

15. Over the past 4 weeks, how **satisfied** have you been with your sexual relationship with your partner?

5 = Very satisfied
4 = Satisfied
3 = Neither satisfied/dissatisfied
2 = Dissatisfied
1 = Very dissatisfied

16. Over the past 4 weeks, how **satisfied** have you been with your overall sex life?

5 = Very satisfied
4 = Satisfied
3 = Neither satisfied/dissatisfied
2 = Dissatisfied
1 = Very dissatisfied

17. Over the past 4 weeks, how **often** have you experienced discomfort or pain during vaginal penetration?

0 = Did not attempt intercourse
1 = Almost always or always
2 = Most of the time (more than half the time)
3 = Some of the time (about half the time)
4 = Occasionally (less than half the time)
5 = Almost never or never

Copyright ©2000 All Rights Reserved.

FSFI - UKEnglish - Final version - 17 Jan 07 - Mapl Research Institute.
ID296

Clinical Investigation Plan

Investigation No:
5025003

Protocol Version:
V3.0 27-Oct-2022

Page 96 of 96

18. Over the past 4 weeks, how often have you experienced discomfort or pain after vaginal penetration?

- 0 = Did not attempt intercourse
1 = Almost always or always
2 = Most of the time (more than half the time)
3 = Some of the time (about half the time)
4 = Occasionally (less than half the time)
5 = Almost never or never

19. Over the past 4 weeks, how would you rate your level (degree) of discomfort or pain during or after vaginal penetration?

- 0 □ = Did not attempt intercourse
 1 □ = Very high
 2 □ = High
 3 □ = Moderate
 4 □ = Low
 5 □ = Very low or none at all

Thank you for completing this questionnaire.

Copyright ©2000 All Rights Reserved

F8F1 - UK/English - Final version - 17 Jan 07 - Mapi Research Institute.
http://www.mapi.es/project/3298/study/339/final_version/infodoku.xls - 17/01/2007

[figure not shown]

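### Does scoring a no-attempt answer as Pain 0 undermine the FSFI responder rate and the 26.55 transition?

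*Combined protocol and SAP*

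**What the plan says.** Section 9.5.1.1 says "The answer choices in the FSFI carry a number of points and are summed to obtain six domain (subscale) scores and an overall score". Each domain sum is then multiplied by a factor. Table 9-1 gives the Pain items (17 to 19) a range of 0 to 5, a factor of 0.4 and a domain minimum of 0. In Appendix 1 the zero option on those items reads "0 = Did not attempt intercourse". Section 9.8 deals with missing items only, and a ticked zero is not missing.

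The FSFI outputs use the Full Analysis Set. Section 9.3 adds a per-protocol analysis for two of them: "total score and percentage of subjects achieving at least a 4-point change in total score". That set drops women who do not meet the "requirements of at least one coital act per week during both the run-in and 4-week IP use period", and also women excluded for product use or other reasons. Section 9.5.1.2 confirms that the analyses of 9.5.1.1 "will be repeated for the PP population".

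For the 26.55 classification, which is tested by McNemar's method, Section 9.5.2.1 states that "the number of subjects categorised as sexual function at 4 weeks will be compared to the number categorised as sexual function at baseline". The same section calls the secondary endpoints supportive and leaves their p-values unadjusted. It also provides that "the FSFI individual domain scores will be summarised as actual scores at baseline and at 4 weeks", including the minimum, and Section 9.6 adds that "subject-level data will be provided in data listings".

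**The concern.** A no-attempt answer carries no information about pain, yet it scores below the most painful measured answer. The run-in forbids lubricant, and Section 7.4.1 foresees occasions when intercourse was not possible without one. A woman could therefore start at Pain 0, resume intercourse with the product, and be counted as a 4-point responder or as having moved out of sexual dysfunction, with no measured reduction in pain. There is no untreated arm against which to judge such cases. The per-protocol set mixes this reason for exclusion with others, and the 26.55 transition is not repeated on it. If such cases were common, both Full Analysis Set rates would be hard to interpret.

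**Working it through.** **1. The plan's own range.** From Table 9-1, the minimum is Desire 2 × 1 × 0.6 = 1.2, plus Satisfaction (0 + 1 + 1) × 0.4 = 0.8, plus 0 for each of the other four domains, giving 2.0. The maximum is 6 × 6 = 36. Both match the table. If every item started at 1, the minimum would be 6 × 1.2 = 7.2. Counting zeros is therefore the stated rule, applied consistently.

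**2. Effect in one woman.** Pain = 0.4 × (sum of items 17 to 19). No attempt gives 0; the worst measured score is 0.4 × 3 = 1.2. A Pain-only gain of 4.0 needs the sum to rise by 4.0 / 0.4 = 10.

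| Baseline Pain sum | Follow-up sum needed | Answer patterns, of 5³ = 125 |
|---|---|---|
| 0 (no attempt) | at least 10 | 53 |
| 3 | at least 13 | 10 |
| 4 | at least 14 | 4 |
| 5 | 15 | 1 |
| 6 or more | not possible | 0 |

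These are counts of patterns, not probabilities. For the cut-off, suppose the other five domains stay at 23.1 and Pain goes from 0 to 4.0: the total goes from 23.1 to 27.1, a transition. With a measured baseline Pain of 2.8 she starts at 25.9 and also transitions; with 3.6 she starts at 26.7 and is already above the cut-off. So the mechanism exists, but crossing 26.55 on Pain alone does not require a zero.

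**3. Who can have a baseline zero.** The FSFI recall is four weeks (Section 6.12.1), so a truthful zero means no attempt in that whole period. One painful or failed attempt gives an answer of 1 to 5. Against this stand:
- weekly intercourse as an entry criterion (Section 4.2.1, criterion 3);
- only mild to moderate dyspareunia at entry (criterion 6);
- the request for weekly intercourse during the run-in (Section 7.4.1);
- the eligibility recheck and diary review at the baseline visit (Section 7.4.2);
- the ban on eligibility waivers (Section 10.4).

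Section 7.4.1 asks for diary entries on individual occasions; it does not describe four weeks without an attempt.

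**4. What is already covered.** A woman with no attempt in the run-in has no coital acts there, so the per-protocol rule excludes her. Both the total score and the 4-point rate are repeated on that set. The 26.55 transition is not.

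**5. Size per case.** Section 4.5 requires 30 completers per arm.
- Mean change: 1.2/30 = 0.04, 4.0/30 = 0.13, 6.0/30 = 0.20. Divided by the 4-point threshold, these are 1%, 3.3% and 5%.
- For scale, the standard deviation is redacted. If the 24 completers and 90% power in Section 3.3 refer to a change of 4 at two-sided 0.025, a paired t-test implies about 5.3. The standard error with 30 women is then 5.3/√30 = 0.97, so 0.20 is about a fifth of it.
- Either rate: 1/30 = 3.3 percentage points. For example, 15/30 = 50.0% (Wilson 95% interval 33.2 to 66.8) against 16/30 = 53.3% (36.1 to 69.8).
- Three cases in one arm would shift a rate by up to 3/30 = 10.0 points and the mean by up to 3 × 0.20 = 0.60.

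**6. Treating the zero as missing is no better.** Take five domains at 4.0 each, total 20. Pro-rating over Pain gives 20 × 6/5 = 24, which credits a Pain score of 4.0 to a woman who attempted no intercourse.

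**The case for a change.** The best case for acting is that zeros at baseline are foreseeable, and that a prespecified table costs a few lines and no new data. A difference between the per-protocol and full-set results could not be attributed to this cause. The Pain minimum and the listings would show that a case exists but would not re-estimate a rate without it. One woman can also matter near a threshold: with hypothetical discordant counts, exact McNemar p goes from 0.063 (5:0) to 0.031 (6:0).

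All of that is factually correct, and the missing per-protocol repeat for the 26.55 transition stands. It does not amount to an error. The McNemar counts are chosen to straddle 0.05, in a test the plan treats as supportive. The obvious sensitivity analysis, dropping baseline zeros, is itself debatable: zeros at Visit 3 pull the other way and would stay in. Dropping zeros at both visits would select on a post-treatment answer. Moving from no intercourse to intercourse may also be a real benefit of a lubricant, which such an analysis would discard. Whether to add the table is a matter of preference.

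**Conclusion.** The concern does not hold. The zero is scored as Table 9-1 specifies, the circumstances that produce it at baseline are screened against at entry and again at Visit 2, and the primary endpoint and the 4-point rate each have a per-protocol repeat that removes such women. At one case per arm of 30, the effect is at most 0.20 points on the mean and 3.3 percentage points on a rate, well inside sampling error. The success criterion in Section 2.2 is framed on the change in total score, not on the 26.55 transition, the one FSFI output discussed here that has no such repeat.

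This rests on cases being few. The documents give no count, but the entry and recheck rules make many cases unlikely. The statement that no further analysis isolates these women is limited to the text available: Section 9.1 leaves detail to the SAP, and the exploratory section (9.5.3) listed in the contents does not appear in it. Followed as written, the plan still supports sound conclusions.

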9.5.1.2 Secondary Analysis

The analyses described in [Section 9.5.1.1](#) will be repeated for the PP population. In addition, for each treatment group, the Total FSFI will be summarised as actual scores at baseline and at 4 weeks, as well as change from baseline for the pre- and post-menopausal subgroups (using the FAS population). No hypothesis testing will be performed for the subgroup analyses.

9.5.2 Secondary Endpoints

9.5.2.1 Secondary Endpoint Analyses

For each of the secondary endpoints, hypothesis testing will not be performed, unless stated otherwise. Since the secondary endpoints are for supportive evidence only, no adjustments to p-values will be made.

The secondary endpoints are:

Treatment Phase:

- Number and percentage of subjects who achieve at least 4-point increase in total FSFI between baseline and 4 weeks.

For each treatment group and overall, the number and percentage of subjects who achieve an improvement of at least 4 points in the FSFI total score will be determined. The percentage and the 95% CI based on the Wilson Score method will be presented.

- Number and percentage of subjects who transition from sexual dysfunction (≤ 26.55 total FSFI score) to sexual function (> 26.55 total FSFI score) between baseline and 4 weeks.

For each treatment group and overall, the number and percentage of subjects who transition from sexual dysfunction (≤ 26.55 total FSFI score) to sexual function (> 26.55 total FSFI score) between baseline and 4 weeks will be determined. Also, the number of subjects categorised as sexual function at 4 weeks will be compared to the number categorised as sexual function at baseline, using McNemar's test. This comparison will be performed by treatment group and overall.

- Change from baseline in the FSFI individual domain scores (desire, arousal, lubrication, orgasm, satisfaction, and pain) at 4 weeks.

For each treatment group, the FSFI individual domain scores will be summarised as actual scores at baseline and at 4 weeks, as well as change from baseline, using n, mean, standard deviation (SD), median, minimum and maximum. Also, for each treatment group, the scores at 4 weeks will be compared to baseline using a paired t-test or Wilcoxon signed rank test, as appropriate.

For this secondary endpoint, the following pairs of hypotheses apply, formulated analogously for all domain scores:

H_0 : The FSFI domain score at Visit 3 of the Treatment Phase shows no difference from the corresponding baseline score.

H_1 : The FSFI domain score at Visit 3 of the Treatment Phase shows a difference from the corresponding baseline score.

Since testing is done within the non-confirmatory secondary endpoints, there is no adjustment for multiple testing.

- SPQs after first use at home and after 4 weeks

For each treatment group, for females and males separately, responses to the SPQ questions will be summarised at each time point (after first use at home and at the end of 4 weeks) as the number and percentage of subjects in each category (Strongly Agree, Agree, Neither Agree or disagree,

Disagree, Strongly Disagree), and also the number and percent in the top 2 categories (Strongly Agree, Agree) for each question.

- Subjects' Global Evaluation of product effectiveness, tolerability and device usability after 4 weeks

For each treatment group, the number and percentage of subjects answering in each category (Greatly Satisfied, Very Satisfied, Moderately Satisfied, Satisfied, Dissatisfied, Very Dissatisfied) will be presented.

- Patient Global Impression of Change at 4 weeks

For each treatment group, for females and males separately, the number and percentage in each of the PGIC categories (-3, -2, -1, 0, +1, +2, +3) at the end of 4 weeks will be summarised using a frequency table. In addition, the number and percentage of subjects who record an improvement of at least 2 points (including a 95% confidence interval calculated using the Wilson score method) will be presented.

Tolerance Phase:

Since only approximately 10 subjects from each treatment group will participate in the Tolerance Phase, all endpoints will be summarised using descriptive statistics only, with no hypothesis testing.

- Vaginal Epithelial Tolerability (none, slight, minimal, moderate, severe)

For each treatment group, the number and percentage of subjects assessed in each category (None, Slight, Minimal, Moderate, Severe) at each time point (baseline, 2 and 24 hours after single use) will be presented.

- Subject Perception of Vulvovaginal Tolerance of the two personal lubricants determined through Subject Perceived Questions at 24 hours post single application.

For each treatment group, the number and percentage of subjects in each category (Strongly Agree, Agree, Neither Agree or disagree, Disagree, Strongly Disagree), and also the number and percent in the top 2 categories (Strongly Agree, Agree) will be presented.

- Global Assessment of Vulvovaginal Tolerance for each subject at 24 hours post single application as determined by the gynaecologist.

At the end of the Tolerance Phase the gynaecologist will make a global assessment of vulvovaginal tolerance, and the number and percentage of subjects in each category (Very Good, Good, Acceptable, Poor, Very Poor) will be presented by treatment group.

- Overall Vulvovaginal Tolerance Rating Statement for each personal lubricant as determined by the gynaecologist.

At the end of the Tolerance Phase, the gynaecologist will make an overall summary assessment of vulvovaginal tolerance of the IP as very well / well / moderately well / not well / not at all well tolerated by all / most / some / a few subjects.

- An assessment of the oral mucosal tolerance of the personal lubricants at baseline, 30 minutes, 2 and 24 hours post single application to the upper and lower inner lip as assessed by dermatologist.

At each timepoint, the number and percentage of subjects in each category (None, Slight, Minimal, Moderate, Severe) will be presented for by treatment group and for each comparator group.

- Subject Perception of Oral Mucosal Tolerance of the two personal lubricants determined through Subject Perceived Questions at 24 hours post single application.

For each treatment group, the number and percentage of subjects in each category (Strongly Agree, Agree, Neither Agree or disagree, Disagree, Strongly Disagree), and also the number and percent in the top 2 categories (Strongly Agree, Agree) will be presented.

- Global Assessment of Oral Mucosal Tolerance for each subject at 24 hours post single application as determined by the dermatologist.

At the end of the Tolerance Phase the gynaecologist will make a global assessment of Oral Mucosal tolerance, and the number and percentage of subjects in each category (Very Good, Good, Acceptable, Poor, Very Poor) will be presented by treatment group.

- Overall Oral Mucosal Tolerance Rating Statement for each personal lubricant as determined by the dermatologist.

At the end of the Tolerance Phase, the gynaecologist will make an overall summary assessment of Oral Mucosal tolerance of each IP and comparator as very well / well / moderately well / not well / not at all well tolerated by all / most / some / a few subjects.

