For the vulvovaginal assessments, subjects will be trained by the site staff on how to apply the IP to the vagina and intimate area and will then make the single application of lubricant at the clinical site in preparation for the 2-hour post application vulvovaginal assessment. For the oral assessments, the clinical site staff will apply a pea-sized application of the IP and the respective comparator to the inner linings of the upper and lower lips of the subject on both sides of the mouth, according to the randomisation schedule. Subjects will be assessed at 30 minutes (± 15 minutes) post application (oral mucosal tolerance only) and 2 hours (± 15 minutes) post application (VET, oral mucosal tolerance, [REDACTED]). In the first 2 hours post application, subjects will be asked to refrain from consuming any foods/drinks. If necessary, subjects may have water, and this will be recorded.

Subject's last menstrual period (the first date and the last date) will be recorded if the data is different from Visit 1. AEs will be collected using a general non-leading question. In addition, spontaneously reported AEs will be collected. Concomitant medication changes will be recorded.

While subjects are at home, they will be instructed to abstain from any vaginal penetrative activity including sexual activity or insertion of tampons and will refrain from using any vaginal products such as moisturisers or intimate washes. They will also be instructed to eat and drink as normal however again will be prohibited from using any new oral products that are irregular to their normal dental hygiene routine or eating any new foods outside their normal diet. Subjects will not be provided with any product to take home as there will be no additional applications during the Tolerance Phase.

All assessments conducted during the Visit 2 are detailed in [Section 6](#) and summarised in Table 7-1. All clinical assessments and test results will be entered into each subject's eCRF.

7.3.3 Visit 3

Subjects will return to the clinical site for their 24-hour assessment. After confirmation of continued eligibility, subjects will undergo the following clinical assessments within the window of 24 hours ± 2 hours:

- Vaginal Epithelial Tolerability (VET), performed by the gynaecologist
- Oral Assessment by the dermatologist
- [REDACTED]
- [REDACTED]

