Subjects will be asked to complete the SPQ – Tolerance Phase at the clinical site. At the end of the Tolerance Phase, the gynaecologist will complete a Global Assessment of Vulvovaginal/Oral Mucosal Tolerance for each subject and provide an Overall Vulvovaginal/Oral Mucosal Tolerance Rating Statement for each IP. The Investigator (in consultation with the gynaecologist and the dermatologist) will determine if the subject remains eligible to enter the Treatment Phase of the investigation, as per the inclusion/exclusion criteria and given that the subject has not experienced any untoward medical occurrence. Additionally, subjects will be issued a diary and instructed to complete during the run-in phase as they enter the Treatment Phase.

Subject's last menstrual period (the first date and the last date) will be recorded if the data is different from Visit 2. AEs will be collected using a general non-leading question. In addition, spontaneously reported AEs will be collected. Concomitant medication changes will be recorded.

All assessments conducted during the Visit 3 are detailed in [Section 6](#) and summarised in Table 7-1. All clinical assessments and test results will be entered into each subject's eCRF.

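### Sections 7.3.3 and 9.5.2.1 give both oral summary ratings to the gynaecologist, while the rest of the protocol gives them to the blinded dermatologist; each section also leaves the comparator out of one rating.

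*Combined protocol and SAP*

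**What the plan says.** **Who rates.** In 9.5.2.1, two oral endpoints have a heading and a body sentence that disagree.

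- Global Assessment. Heading: "Global Assessment of Oral Mucosal Tolerance for each subject at 24 hours post single application as determined by the dermatologist". Body: "At the end of the Tolerance Phase the gynaecologist will make a global assessment of Oral Mucosal tolerance".
- Overall Rating Statement. Heading: "Overall Oral Mucosal Tolerance Rating Statement for each personal lubricant as determined by the dermatologist". Body: "the gynaecologist will make an overall summary assessment of Oral Mucosal tolerance of each IP and comparator".

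Section 7.3.3 (Visit 3) sides with the body sentences: "the gynaecologist will complete a Global Assessment of Vulvovaginal/Oral Mucosal Tolerance for each subject". The same sentence has the gynaecologist "provide an Overall Vulvovaginal/Oral Mucosal Tolerance Rating Statement for each IP". Yet the list of 24-hour assessments in 7.3.3 reads "Oral Assessment by the dermatologist".

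The synopsis (secondary endpoints, and methodology for Tolerance Phase Visit 3), Table 2-1, 6.11.5 and 6.11.6 all name the dermatologist. Sections 5.6 and 6.4.1.2 say that the oral tolerance assessments are done by a dermatologist who stays blinded to the randomisation. Section 5.6 also says that the products themselves are not masked. No blinding is stated for the gynaecologist, and 6.7 assigns the oral examination to the dermatologist.

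**Which products.** Section 6.11.5 calls for a Global Assessment of each IP and comparator, but 9.5.2.1 presents it by treatment group only. For the timed oral sign scores, 9.5.2.1 adds the comparator explicitly: "will be presented for by treatment group and for each comparator group". For the Overall Statement, 7.3.3 covers each IP; the synopsis methodology, 6.11.6 and the 9.5.2.1 body cover each IP and comparator.

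**The concern.** Site staff work from the visit instructions and the programmer works from the analysis section, and these are the two places that name the gynaecologist. Followed literally, they move two oral endpoints from the blinded examiner to a rater with no stated blinding and no assigned oral examination. In an open-label study, the blinded dermatologist is the one measure that 5.6 offers against evaluation bias, and these two ratings would lose it.

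The comparator is in the Tolerance Phase so that the sensate products can be set against non-sensate ones in the mouth (1.3, 3.2), and 6.3 randomises the side of the mouth for that purpose. If the comparator is left out of the Global Assessment table or the Overall Statement, that summary does not show the contrast.

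**Working it through.** This is a check of text and counts. No sample size, power or significance level is involved.

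**Step 1: rater named, for each oral summary rating**

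| Place | Global Assessment | Overall Statement |
|---|---|---|
| Synopsis, secondary endpoints | dermatologist | dermatologist |
| Synopsis, methodology, Visit 3 | dermatologist | dermatologist |
| Table 2-1 | dermatologist | dermatologist |
| 6.11.5 / 6.11.6 | dermatologist | dermatologist |
| 9.5.2.1, heading | dermatologist | dermatologist |
| 7.3.3 | gynaecologist | gynaecologist |
| 9.5.2.1, body | gynaecologist | gynaecologist |

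For each rating, 5 places name the dermatologist and 2 the gynaecologist. Table 7-1 schedules both ratings without naming a rater, so it does not settle the matter. Section 9.5.2.1 has 4 oral endpoints (timed sign scores, subject perception, Global Assessment, Overall Statement), and the rater conflicts in 2 of the 4.

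**Step 2: likely source.** The oral body sentences in 9.5.2.1 closely repeat the vulvovaginal sentences above them, where the gynaecologist is the right rater. Section 7.3.3 merges the two sites with a slash. Both patterns suggest carried-over wording.

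**Step 3: products covered**

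- Overall Statement: IP and comparator in 3 places (synopsis methodology, 6.11.6, 9.5.2.1 body); each IP only in 7.3.3, which is 2 of the 4 products.
- Global Assessment: 2 IPs + 2 comparators = 4 products under 6.11.5; 2 treatment groups named for tabulation in 9.5.2.1.

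**Step 4: ratings without a specific table.** Inputs: 22 women enter the Tolerance Phase with 10% attrition (3.3), and each tests one IP and its comparator (6.4.1.2).

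- Completers: 22 × 0.9 = 19.8, about 20, matching the protocol's own figure.
- One rating per product, as in 6.11.5: 20 × 2 = 40 ratings, of which 20 are for comparators. If all 22 complete: 22 × 2 = 44, of which 22.
- One rating per woman, as the for-each-subject wording elsewhere could be read: about 20 ratings, all covered by the treatment-group table, with no separate comparator rating.

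The count of comparator ratings without a specific table is therefore about 20 (22 at most) under 6.11.5 and zero under the other reading. The protocol does not say which reading governs.

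**The case against.** The strongest reply is that the protocol largely answers the rater question itself. Section 7.3.3 refers to Section 6 for the details of its assessments, Section 6 names the dermatologist for both ratings, and 6.4.1.2 makes the same blinded dermatologist mandatory for the oral tolerance assessments. The 9.5.2.1 headings agree. This stands: the intended rater is reasonably clear. A reader might treat the 9.5.2.1 body sentences as the text that governs, but nothing in the protocol gives them that rank. What remains is that the visit instruction and the analysis text both say otherwise.

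Second, the blinding at stake is limited. Sections 5.6 and 6.4.1.2 do not say expressly that it extends to the two summary ratings. The Global Assessment also draws on the women's own questionnaire answers, and the Overall Statement is made per product, with no coded grouping described in the visible text. This also stands: the safeguard is partial even with the dermatologist.

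Third, 9.6 promises descriptive summaries where appropriate as well as listings, and 9.1 leaves analysis details to a separate SAP that is not visible here. A reader might infer that comparator ratings would appear only in subject listings, or that no comparator table is planned; the documents support neither. They support only that no specific table is stated, while the timed sign scores in the same section do have one.

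**Conclusion.** The contradiction on the rater is certain: two oral endpoints, five places against two for each. The conflict on product coverage is equally plain in the text. Its size, about 20 comparator ratings from 20 completers without a specific table, depends on following 6.11.5 rather than the for-each-subject wording.

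The effect is contained. Both endpoints are secondary and descriptive, in a 22-woman subset. The timed oral sign scores stay with the dermatologist and keep their comparator groups, and the primary Female Sexual Function Index (FSFI) analysis is untouched. The point is still more than a typing slip, because the literal text takes two ratings away from the blinded examiner.

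A reader might go on to infer that the women's own perception of the comparator is not collected or analysed. The documents do not support that: the questionnaire items and some neighbouring sections are not visible, so nothing is claimed about it.

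**What to change.** 1. In 7.3.3 and in the two oral body sentences of 9.5.2.1, name the blinded dermatologist for the Global Assessment and the Overall Rating Statement. Make the 7.3.3 statement cover each IP and comparator.
2. In 9.5.2.1, tabulate the oral Global Assessment for each IP and each comparator, as is already planned for the timed sign scores. State in 7.3.3 that one Global Assessment is given per product.

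The cost is wording in two sections and comparator columns in one table, with no new staff or visits.
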